To evaluate the effect of baricitinib 4-mg QD and background SoC therapy compared to placebo and SoC on SLE disease activity	
 • Proportion of patients achieving an SRI-4 response at Week 52, defined as: 
 • a reduction of ≥ 4 points from baseline in SLEDAI-2K score, and • No new BILAG A and no more than 1 new BILAG B disease activity score, and • No worsening (defined as an increase of ≥ 0.3 points [10 mm] from baseline) in the PGA of Disease Activity.
Major Secondary^c	
To evaluate the effect of baricitinib 4-mg QD plus SoC compared to placebo plus SoC on SLE disease activity	
 • Proportion of patients achieving an SRI-4 response at Week 24 • Proportion of patients achieving a LLDAS response at Week 52
To evaluate the corticosteroid sparing effect of baricitinib 4-mg QD plus SoC compared to placebo plus SoC	
 • Proportion of patients receiving >7.5 mg prednisone (or equivalent) at baseline able to decrease dose by $\geq 25\%$ to a prednisone equivalent dose of ≤ 7.5 mg/day maintained between Week 40 and Week 52
To evaluate the effect of baricitinib 4-mg QD plus SoC compared to placebo plus SoC on SLE flares	
 • Time to first severe flare over 52 weeks
To evaluate the effect of baricitinib 4-mg QD plus SoC compared to placebo plus SoC on PROs	
 • Change from baseline in Worst Pain NRS at Week 52 • Change from baseline in FACIT-Fatigue total score at Week 52

Primary and Major Secondary Objectives and Endpoints

Objectives	Endpoints (Variables)^a
To evaluate the effect of baricitinib 2-mg QD plus SoC compared to placebo plus SoC on SLE disease activity	
 • Proportion of patients achieving an SRI-4 response at Week 52 • Proportion of patients achieving an SRI-4 response at Week 24 • Proportion of patients achieving a LLDAS response at Week 52
To evaluate the corticosteroid sparing effect of baricitinib 2-mg QD plus SoC compared to placebo plus SoC	
 • Proportion of patients receiving >7.5 mg prednisone (or equivalent) at baseline able to decrease dose by $\geq 25\%$ to a prednisone equivalent dose of ≤ 7.5 mg/day maintained between Week 40 and Week 52

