Treatment comparisons for duration of joint stiffness will be analyzed using a nonparametric method using the Hodges-Lehmann estimator. For the comparison between each baricitinib group and placebo group, the median difference of change from baseline score and its 95% CI from the Hodges-Lehmann estimator will be presented. The p-value for the median difference of change from baseline will be calculated using the Wilcoxon rank-sum test. A 95% CI for the median change from baseline score within each treatment group will be calculated using distribution-free confidence limits.

Time to first flare analyses will be analyzed using a Cox proportional hazards model with treatment group, with disease activity (total SLEDAI-2K <10; \geq 10), baseline corticosteroid dose (<10 mg/day; \geq 10 mg/day prednisone or equivalent), and region (North America, Central/South America/Mexico, Europe, Asia and Rest of World) fitted as explanatory variables. Hazard ratios, median time to flare, 95% CI and p-values will be presented for treatment comparisons to placebo. Only if flares occurred during the flare exposure time period (defined below for each datapoint set, respectively) will be counted as an event. For severe SFI flare, only the eligible severe flares will be counted (See 6 criteria for identifying eligible severe SFI flares in [Appendix 5](#)). Patients who do not have an event during the flare exposure time period will be censored at the end of the flare exposure time. The flare exposure time varies with different datapoint sets ([Table JAIA.6.5](#)).

- For the PPCV datapoint set, while considering the treatment effect without potentially confounding influences of COVID-19, the flare exposure time is defined as the time after the date of the first dose of study drug to the prohibited medication start date, treatment discontinuation date, study discontinuation date or date of the Week 52 visit, whichever is earlier, and excluding the time period of treatment interruption due to COVID-19 from the interruption start date plus 20 days to the interruption end date plus 20 days, both inclusive, if the interruption duration is 20 days or more.

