6.6 Multiple Comparisons/Multiplicity

A prespecified graphical multiple testing approach (Bretz et al. 2009, 2011) will be implemented to control the overall Type I error rate at 2-sided alpha of 0.05, for all primary and major secondary endpoints. The graphical approach is a closed testing procedure; hence, it strongly controls the familywise error rate across all endpoints (Alosh et al. 2014). Details of the graphical testing scheme (including testing order, interrelationships, Type I error allocation, and the associated propagation) are included below (see [Figure JAIA.6.1](#)). Each hypothesis is represented as a node in a graph. Directed arrows between the nodes with associated weights represents how alpha is passed from its initial allocation to other nodes. The testing scheme was finalized before the first unblinding of the study team to efficacy data. Unless otherwise specified, there will be no adjustment for multiple comparisons for any other analyses.

Abbreviations: FACIT-F = Functional Assessment of Chronic Illness Therapy-Fatigue; LLDAS = Lupus Low Disease Activity State; SRI-4 = Systemic Lupus Erythematosus Responder Index-4; TTE = time to event; W = week.

Note: All tests are compared to placebo. All hypothesis tests contained within a box must be rejected before alpha is passed on.

Figure JAIA.6.1. **Illustration of graphical multiple testing procedure with initial α allocation and weights.**

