CLASI	
The CLASI is a validated instrument to assess cutaneous manifestations of SLE consisting of 2 scores:
 
 Activity Damage 	Total Activity Score	Calculated within tablet system with edit checks; no additional derivation.	
Within tablet system: If any item scores, but not all are missing then impute a score of 0 for the missing item(s).
 
For completely missing questionnaires, data can be carried forward if obtained within 36 days of visit; otherwise missing.

		Total Damage Score	Calculated within tablet system with edit checks; no additional derivation.	
Within tablet system: if any item scores, but not all are missing then impute a score of 0 for the missing item(s).
 
For completely missing questionnaires, data can be carried forward if obtained within 36 days of visit; otherwise missing.

Description and Derivation of Efficacy/Health Outcomes Measures and Endpoints

Measure	Description	Variable	Derivation/Comment	Definition of Missing
LLDAS	The LLDAS is a composite measure designed to identify patients achieving a state of low disease activity.	LLDAS	
 SLEDAI-2K \leq 4, with no activity in SLEDAI-2K major organ systems (CNS, Vascular, Renal, Cardiorespiratory and Constitutional), where “no activity” is defined as all items of SLEDAI-2K within these major organ systems equal to 0. No new features of Lupus disease activity in SLEDAI-2K compared to previous occurred visit, where the “new feature” is defined as any of the SLEDAI-2K 24 items changed from 0 to greater than 0. PGA \leq 1 Current prednisone or equivalent \leq 7.5 mg/day 	Missing if any component remains missing after each instrument level imputation rule is applied.
SFI Flare	The SFI uses the SLEDAI score, disease activity scenarios, treatment changes, and PGA to define mild/moderate and severe flares.	SFI Flare	Not derived; used as entered.	The absence of a flare record, or ‘Not Applicable’, both are indicative of no occurrence of flare.
		Annualized Flare Rate	Calculated as the number of SFI flares divided by the flare exposure time in days multiplied with 365.25.	No minimum data requirement.
		Time to First Flare	The time to first flare will be derived as the first date of most recent flare minus date of first administration of investigational product. If the subject did not have a flare, the time to first flare will be censored at the end of the flare exposure time	No minimum data requirement.

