	Proportion of patients with worsening in each BILAG individual organ systems versus baseline ^e	Logistic Regression, NRI	PP	Week 52 visit	Exploratory endpoint
PGA	Proportion of patients with no worsening in PGA (compared with baseline)	Logistic Regression, NRI+MI	PPCV	Week 52 visit	Secondary endpoint
		Logistic Regression, NRI	PP	Week 52 visit	Secondary endpoint
	Change from baseline in PGA score over time through Week 52 visit	MMRM	PP	Week 52 visit	Secondary endpoint
BICLA	Proportion of patients achieving BICLA response	Logistic Regression, NRI + MI	PPCV	Week 52 visit	Secondary endpoint
		Logistic Regression, NRI	PP	Week 52 visit	Secondary endpoint
		Logistic Regression, NRI	AC	Week 52 visit	Secondary endpoint

Description of Efficacy/Health Outcomes Analyses

Measure	Variable	Analysis and Imputation Method	Datapoint Sets	TPI*	Analysis Type
28 Tender/ Swollen Joint Count	Change from baseline in tender joint count	MMRM	PP	Week 52 visit	Secondary endpoint
	Change from baseline in swollen joint count	MMRM	PP	Week 52 visit	Secondary endpoint
CLASI Activity Score	The proportion of patients with \geq 50% reduction from baseline in total activity score ^f	Logistic Regression, NRI	PP	Week 52 visit	Secondary endpoint
SFI	Annualized severe flare rate	Negative binomial regression	PPCV	Through Week 52 visit	Secondary endpoint
		Negative binomial regression	PP		Supplemental
		Negative binomial regression	AC		Supplemental
	Annualized mild/moderate flare rate	Negative binomial regression	PP	Through Week 52 visit	Secondary endpoint
	Annualized flare rate (any severity)	Negative binomial regression	PP	Through Week 52 visit	Secondary endpoint
	Time to first severe flare	Cox regression	PPCV	Through Week 52 visit	Major secondary (Principal inference)
			PP		Supplemental
			AC		Supplemental
	Time to first flare (any severity)	Cox regression	PP	Through Week 52 visit	Secondary endpoint
LLDAS	Proportion of patients who achieve a LLDAS	Logistic Regression, NRI + MI	PPCV	Week 52 visit	Major secondary (Principal inference)
		Logistic Regression, NRI	PP		Supplemental
		Logistic Regression, NRI	AC		Supplemental

Description of Efficacy/Health Outcomes Analyses

Measure	Variable	Analysis and Imputation Method	Datapoint Sets	TPI*	Analysis Type

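### Table JAIA.6.4 dates time to first flare from the most recent flare; the sentence should name the earliest countable flare

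*SAP*

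**What the plan says.** The SFI Flare row of SAP Table JAIA.6.4 (Section 6.10.1) contains a variable called Time to First Flare and gives this derivation for it: "The time to first flare will be derived as the first date of most recent flare minus date of first administration of investigational product". Its next sentence censors patients without a flare at the end of the flare exposure time.

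Other places that bear on the endpoint:

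- Table JAIA.4.1 lists "Time to first severe flare over 52 weeks" as a major secondary endpoint for each dose. Table JAIA.6.6 makes the PPCV analysis of it the principal inference.
- Section 6.6 places it under a graphical procedure to "control the overall Type I error rate at 2-sided alpha of 0.05, for all primary and major secondary endpoints".
- Time to first flare of any severity is an other secondary endpoint in Table JAIA.4.1, outside multiplicity control. It uses the same derivation row.
- Section 6.4 fixes the model: "Time to first flare analyses will be analyzed using a Cox proportional hazards model with treatment group", plus the stratification factors. It counts only flares inside the flare exposure time, and adds: "For severe SFI flare, only the eligible severe flares will be counted". On censoring: "Patients who do not have an event during the flare exposure time period will be censored at the end of the flare exposure time".
- Appendix 5 sets out which severe flares are eligible.
- The annualized flare rate, in the same row of Table JAIA.6.4, is "Calculated as the number of SFI flares divided by the flare exposure time in days multiplied with 365.25". The plan therefore expects some patients to flare more than once.

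**The concern.** The variable is named for the first flare, but its formula dates the most recent one. Section 6.4 and Appendix 5 say which flares count and when exposure ends. Neither says which of several counted flares supplies the date, so the table's formula is the operative rule.

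A program that follows it gives the right time to patients with one flare and too late a time to patients with two or more. If repeat flares are more common on the less effective arm, event times there are delayed more, and the hazard ratio moves toward 1. The reported median time to flare would also be too long. One of the affected endpoints carries alpha, so its derivation should not depend on a programmer guessing the intent.

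**Working it through.** **1. Reading the rule.** Take a patient with countable flares on days 40, 150 and 300. The literal formula gives 300 days; time to first flare is 40 days. For flares inside the exposure time, the event and censoring indicators are the same either way. Only the event time differs, and only for patients with two or more countable flares.

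**2. The plan's own figure.** The SAP gives no flare rate, hazard ratio or event count. Its only power statement (Section 5.2) is for SRI-4: over 90% for 40% against 57%, with about 750/3 = 250 patients per arm and two-sided 0.05. The two-proportion formula gives 96.9%, so that figure stands. It says nothing about flares, so the rates below are assumptions.

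**3. Share of flaring patients affected.** For Poisson flares at rate λ over one year, the share of flaring patients with two or more is

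P(N ≥ 2 | N ≥ 1) = 1 − λ/(e^λ − 1).

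- λ = 0.2: 1 − 0.2/0.2214 = 9.7%
- λ = 1.0: 1 − 1/1.7183 = 41.8%

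Variation in flare rate between patients raises these shares.

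**4. Effect on the Cox model.** Two sets of simulated two-arm trials were run, with 250 per arm and one year of full follow-up. Each trial was analysed once with the first flare date and once with the last.

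*Set A: gamma-Poisson flares, rate ratio 0.70, 300 trials per scenario*

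| Assumed rate per year | Event patients misdated | Hazard ratio, first to last |
|---|---|---|
| 0.2–0.3 (severe) | 9–21% | 0.70–0.72, change under 0.01 |
| 1.0–1.5 (any severity) | 42–54% | 0.73 to 0.76; 0.75 to 0.80 |

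*Set B: rate ratio 0.65, 400 trials per scenario. Dispersion 0 is Poisson; dispersion 1 is gamma-Poisson. The rate is for placebo.*

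| Rate | Dispersion | With repeats | Hazard ratio, first to last | Power, first to last | Median event time (days), first to last |
|---|---|---|---|---|---|
| 0.2 | 0 | 8.4% | 0.661 to 0.662 | 41.8% to 40.5% | 174 to 190 |
| 0.2 | 1 | 14.6% | 0.660 to 0.662 | 39.2% to 38.0% | 168 to 196 |
| 0.4 | 0 | 16.0% | 0.649 to 0.654 | 70.2% to 69.2% | 166 to 197 |
| 0.4 | 1 | 25.4% | 0.686 to 0.693 | 52.8% to 49.5% | 157 to 209 |
| 1.0 | 0 | 36.2% | 0.653 to 0.682 | 94.5% to 89.8% | 145 to 219 |
| 1.0 | 1 | 45.2% | 0.716 to 0.744 | 72.2% to 61.8% | 130 to 236 |
| 2.0 | 0 | 60.9% | 0.652 to 0.763 | 99.5% to 79.0% | 114 to 252 |
| 2.0 | 1 | 61.9% | 0.742 to 0.806 | 73.2% to 47.8% | 101 to 265 |

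The median event time is among patients with a flare. At severe-like rates (0.2–0.4) the largest hazard-ratio change is 0.693 − 0.686 = 0.007, and power falls by about 1 to 3 points. At any-severity-like rates (1.0–2.0) power falls by about 5 to 25 points.

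**5. Early end of exposure.** Both sets assume a full year at risk. In PPCV and PP, exposure stops at prohibited medication or treatment discontinuation. Two severe-flare criteria in Appendix 5, a prednisone increase and the start of an immunosuppressant, are changes that Table JAIA.6.2 generally does not permit after baseline. Such a flare can itself close the window. As an illustration, if half of first severe flares did so, the share at λ = 0.2 would fall from 9.7% to about 0.5 × 9.7% = 4.9%.

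**The case against.** The strongest defence is that this is a slip of wording. The name of the variable, Tables JAIA.4.1 and JAIA.6.6, Section 6.4 and Appendix 5 all speak of the first flare, so a competent programmer would probably use the earliest date. The phrase may also mean the earliest value in a recorded field for the most recent flare, since the same row says that SFI flares are used as entered. That reading would normally return the first flare. It is possible, but the SAP describes no such field, and a formula with two readings that give different event times still needs correcting.

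A reader might infer more than the SAP supports:

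- **That the window and eligibility rules are missing.** They are not. Section 6.4 limits events to the flare exposure time and severe flares to those eligible under Appendix 5. The table row need not repeat this.
- **That an earlier flare is lost when two fall between forms.** This assumes a form layout that the SAP does not describe.
- **That the multiplicity-controlled result is materially distorted.** At the assumed severe-flare rates it is not. The larger shifts concern the any-severity endpoint only.
- **That the error favours the drug.** With a real benefit and more repeat flares on placebo, the hazard ratio moves toward 1. With identical flare processes in the arms, last-flare times have the same distribution in each, so the rule gives neither arm an advantage.

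**Conclusion.** The point holds as an error of definition. The only event-time formula for time to first flare names the wrong flare when read plainly, and nothing elsewhere in the SAP corrects it. It should be fixed because one of the two endpoints that use it is multiplicity-controlled, although the numerical effect on that endpoint is small: a hazard-ratio change under 0.01 at assumed rates of 0.2 to 0.4 severe flares per year, and probably less in PPCV and PP. For any-severity flare the effect is material at assumed rates of 1 to 2 per year, toward 1, with a loss of power and a median event time later by 74 days (219 − 145) to 164 days (265 − 101).

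These sizes rest on assumed flare rates, rate ratios of 0.65 and 0.70, 250 patients per arm and full follow-up. The contradiction in the text rests on none of them. The documents do not show that the sponsor intended to analyse the last flare, or that any program did so.

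**What to change.** In the Time to First Flare row of Table JAIA.6.4, replace the derivation with: start date of the earliest flare counted under Section 6.4 (within the flare exposure time of the datapoint set and, for severe flares, eligible under Appendix 5) minus the first-dose date, derived from all flare records. Section 6.4, Appendix 5, the censoring rule and the sample-size statement stay as they are.

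The cost is one sentence and a check that the analysis program takes the minimum, not the maximum, of the eligible flare dates. If the analysis has already been programmed or run, that check settles whether any result is affected.

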Measure	Description	Variable	Derivation/Comment	Definition of Missing
Steroid sparing	This measures the proportion of patients who, having a high enough dose at baseline, are able to reduce steroids to a certain level.	Receiving >7.5 mg prednisone (or equivalent) at baseline and able to decrease dose by $\geq 25\%$ to a prednisone equivalent dose of ≤ 7.5 mg/day maintained between the Week 40 visit and the Week 52 visit	Dose reduction must be greater than or equal to baseline dose $\times .25$ and achieve a dose of less than or equal to 7.5 mg per day perpetually between the Week 40 visit and Week 52 visit.	No minimum data requirement.
		Receiving >7.5 mg prednisone (or equivalent) at baseline and able to decrease dose by $\geq 25\%$ by the Week 52 visit	Dose reduction must be greater than or equal to baseline dose $\times .25$ per day perpetually between the Week 40 visit and the Week 52 visit.	No minimum data requirement.
		Receiving >7.5 mg prednisone (or equivalent) at baseline and able to decrease to a prednisone equivalent dose of ≤ 7.5 mg/day by the Week 52 visit	Dose reduction must be less than or equal to 7.5 mg per day perpetually between the Week 40 visit and the Week 52 visit.	No minimum data requirement.
		Receiving prednisone (or equivalent) at baseline and able to discontinue and maintain through the Week 52 visit	Among patients with baseline prednisone (or equivalent) dose >0 mg and able to reduce the dose to 0mg at some time point and then maintained at 0mg from that time through the Week 52 visit.	No minimum data requirement.
Worst Joint Pain NRS	This Worst Joint Pain NRS is a single-item, patient-administered 11-point horizontal scale anchored at 0 (no joint pain) and 10 (joint pain as bad as you can imagine)	Worst Joint Pain NRS Score	Calculated by averaging data for all available daily diary entries for a 7-day period prior to the visit, not inclusive of the clinic visit day.	Missing if fewer than 4 available daily measurements in the relevant 7 days

Description and Derivation of Efficacy/Health Outcomes Measures and Endpoints

Measure	Description	Variable	Derivation/Comment	Definition of Missing

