Corticosteroid Sparing	Proportion of patients receiving > 7.5 mg/day prednisone at baseline able to reduce prednisone (or equivalent) dose by $\geq 25\%$ to a prednisone equivalent dose of ≤ 7.5 mg/day maintained between Week 40 and Week 52 visit ^g	Logistic Regression, NRI + mLOCF	PPCV	Week 52 visit	Major secondary (Principal inference)
		Logistic Regression, NRI	PP		Supplemental
		Logistic Regression, NRI	AC		Supplemental
	Proportion of patients receiving > 7.5 mg/day prednisone at baseline able to reduce prednisone (or equivalent) dose by $\geq 25\%$ maintained between Week 40 and Week 52 visit ^g	Logistic Regression, NRI + mLOCF	PPCV	Week 52 visit	Supplemental
		Logistic Regression, NRI	PP		Supplemental
	Proportion of patients receiving > 7.5 mg/day prednisone at baseline able to reduce prednisone (or equivalent) dose to ≤ 7.5 mg/day maintained between Week 40 and Week 52 visit ^g	Logistic Regression, NRI + mLOCF	PPCV	Week 52 visit	Supplemental
		Logistic Regression, NRI	PP		Supplemental
	Change from baseline in prednisone dose	MMRM	PP	Week 52 visit	Secondary endpoint
	Proportion of patients able to discontinue corticosteroids and maintained through Week 52 visit ^h	Logistic Regression, NRI	PP	Week 52 visit	Secondary endpoint
Worst Pain NRS	Change from baseline in Worst Pain NRS	MMRM+MI	PPCV	Week 52 visit	Major secondary (Principal inference)
		MMRM	PP		Supplemental
		MMRM	AC		Supplemental

Description of Efficacy/Health Outcomes Analyses

Measure	Variable	Analysis and Imputation Method	Datapoint Sets	TPI*	Analysis Type
FACIT-Fatigue	Change from baseline in FACIT-Fatigue total score	MMRM+MI	PPCV	Week 52 visit	Major Secondary (Principal inference)
		MMRM	PP		Supplemental
		MMRM	AC		Supplemental
Worst Fatigue NRS	Change from baseline in Worst Fatigue NRS	MMRM	PP	Week 52 visit	Secondary endpoint
Worst Joint Pain	Change from baseline in Worst Joint Pain NRS	MMRM	PP	Week 52 visit	Secondary endpoint
Joint Stiffness Duration	Change from baseline in Joint Stiffness Duration	Wilcoxon rank-sum with mLOCF	PP	Week 52 visit	Secondary endpoint
Joint Stiffness Severity	Change from baseline in Joint Stiffness Severity	MMRM	PP	Week 52 visit	Secondary endpoint
Patient Global Impression of Severity	Change from baseline in Patient Global Impression of Severity	MMRM	PP	Week 52 visit	Secondary endpoint
Patient Global Impression of Change	Change from baseline in Patient Global Impression of Change	ANOVA with mLOCF	PP	Week 52 visit	Secondary endpoint

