- ^c Population is a subset of mITT which includes patients with at least one SLEDAI-2K item = 0 in the organ domain at baseline.
- ^d Population is a subset of mITT which includes patients with BILAG A or B in the organ domain at baseline.
- ^e Population is a subset of mITT which includes patients without BILAG A in the organ domain at baseline.
- ^f Population is a subset of mITT which includes patients with CLASI total activity score ≥ 10 at baseline.
- ^g Population is a subset of mITT which includes patients with > 7.5 mg/day prednisone at baseline. The logistic regression model covariates include treatment groups, baseline disease activity (total SLEDAI-2K <10 ; ≥ 10) and region (North America, Central/South America/Mexico, Europe, Asia and Rest of World).
- ^h Population is a subset of mITT which includes patients with > 0 mg/day prednisone at baseline.
- ⁱ For absenteeism score, presenteeism score, and work productivity loss score, population is a subset of mITT which includes patients who had employment status of Yes at baseline.
- * Assessments collected at multiple visits will be analyzed at each visit, in addition to the primary time point listed in the table.

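### The derivation of the supplemental steroid-sparing variable for reaching 7.5 mg/day or less caps the size of the dose cut instead of the dose reached, contradicting its own name and Table JAIA.6.6

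*SAP*

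**What the plan says.** SAP Section 6.10.1, Table JAIA.6.4, defines four steroid-sparing variables. The first three concern patients above 7.5 mg/day prednisone (or equivalent) at baseline.

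- **First variable** (major secondary): a cut of at least 25% to a dose of 7.5 mg/day or less. The derivation states two conditions separately. The cut is "Dose reduction must be greater than or equal to baseline dose" times .25, and the patient must also reach the level: "and achieve a dose of less than or equal to 7.5 mg per day perpetually".
- **Second variable:** the 25% cut alone. It uses the same opening phrase and the same comparison with a quarter of the baseline dose.
- **Third variable:** the level alone. The variable column says the patient is "able to decrease to a prednisone equivalent dose of" 7.5 mg/day or less. The derivation column says: "Dose reduction must be less than or equal to 7.5 mg per day perpetually between the Week 40 visit and the Week 52 visit".

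Table JAIA.6.6 lists the third variable as patients "able to reduce prednisone (or equivalent) dose to" 7.5 mg/day or less, maintained between Week 40 and the Week 52 visit. It is analysed by logistic regression in the PPCV and PP datapoint sets and labelled supplemental in both. Footnote g restricts the analysis to the mITT subset above 7.5 mg/day at baseline.

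**The concern.** The variable name and Table JAIA.6.6 limit the dose the patient ends on. The derivation limits how much the dose came down. These are different rules, and for many patients they give opposite answers.

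The SAP introduces Table JAIA.6.4 as the source of derivations, so this is the cell a programmer would implement. The variable does not appear in Table JAIA.4.1, so Tables JAIA.6.4 and JAIA.6.6 are its only definition in this document. Followed literally, the analysis would credit patients who barely taper and fail those who taper most. The supplemental result on reaching 7.5 mg/day would then not describe the variable it is named for.

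**Working it through.** The SAP gives no figure to reproduce, so the check is a comparison of two rules.

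**Inputs**
- B = baseline prednisone-equivalent dose, with B > 7.5 mg/day (Table JAIA.6.6, footnote g).
- D = daily dose held from the Week 40 visit to the Week 52 visit.
- Range of B: Table JAIA.6.2 allows baseline oral corticosteroid up to 40 mg/day, so 40 is the upper end of the check.

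**Rules**
- Named variable and Table JAIA.6.6: success if D ≤ 7.5.
- Derivation as written: success if B − D ≤ 7.5, that is, D ≥ B − 7.5.

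**When both can be met.** Both hold only if B − 7.5 ≤ D ≤ 7.5, which requires B ≤ 15. For B > 15, any D ≤ 7.5 gives B − D > 7.5, so no true success survives.

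**Worked cases (mg/day)**

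| Baseline to later dose | Cut | Named variable | As written |
|---|---|---|---|
| 20 to 5 | 15 | success | failure |
| 40 to 35 | 5 | failure | success |
| 30 to 15 | 15 | failure | failure |
| 10 to 10 | 0 | failure | success |
| 10 to 0 | 10 | success | failure |
| 10 to 5 | 5 | success | success |

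**Full classification on a 0.5 mg grid of D from 0 to B**

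| B | Grid values | True success scored failure | True failure scored success | Failure under both | Success under both |
|---|---|---|---|---|---|
| 10 | 21 | 5 (D 0 to 2) | 5 (D 8 to 10) | 0 | 11 (D 2.5 to 7.5) |
| 15 | 31 | 15 (D 0 to 7) | 15 (D 8 to 15) | 0 | 1 (D 7.5) |
| 20 | 41 | 16 (D 0 to 7.5) | 16 (D 12.5 to 20) | 9 (D 8 to 12) | 0 |
| 30 | 61 | 16 (D 0 to 7.5) | 16 (D 22.5 to 30) | 29 (D 8 to 22) | 0 |
| 40 | 81 | 16 (D 0 to 7.5) | 16 (D 32.5 to 40) | 49 (D 8 to 32) | 0 |

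These count grid values, not patients. They show which outcomes change, not how often.

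**Consistency with the major secondary endpoint.** The first variable is the second and third combined, so each of its successes should also be a success on the third. A patient going from 20 to 5 mg/day meets the first (cut 15 ≥ 0.25 × 20 = 5; dose 5 ≤ 7.5) but fails the third as written (cut 15 > 7.5).

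**Overlap with the major secondary endpoint.** Reaching D ≤ 7.5 means a cut of at least B − 7.5. This is at least 0.25B when 0.75B ≥ 7.5, that is, when B ≥ 10. From 10 mg/day upward the third variable as named therefore gives the same answer as the first. They can differ only for 7.5 < B < 10; for example, 8 to 7 mg/day reaches the level with a cut of 1, below 0.25 × 8 = 2.

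**The case against.** The strongest reply is that this is a drafting slip whose intended meaning is not in doubt. The variable column beside the derivation, the measure's description, Table JAIA.6.6 and the first row all point to the dose reached. An attentive programmer would probably read the phrase as the reduced dose. A literal implementation would also show itself, because major secondary successes would fail a variable they must satisfy. This stands, and it limits the seriousness. It does not make the derivation correct: the two rows above use the same phrase for the size of the cut, and the first row words the dose cap separately.

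Nothing confirmatory is touched either. The variable is supplemental, and from 10 mg/day upward the correctly worded major secondary endpoint already gives the intended answer. That also stands.

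A reader might make three stronger inferences that the documents do not support:

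- **That successes and failures are reversed for every patient above 15 mg/day.** Only true successes all change. A failure becomes a success only when the cut is 7.5 mg or less; at a baseline of 40, any dose strictly between 7.5 and 32.5 fails under both rules.
- **That the damage stops at 15 mg/day.** It does not; lower baselines are misclassified in both directions. Fifteen is only the point above which no true success survives.
- **That the multiplicity-controlled sparing result is at risk.** Its derivation caps the dose reached and is correctly worded.

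**Conclusion.** The point holds as an internal contradiction in the derivation of one supplemental variable. Followed as written, every true success above 15 mg/day at baseline is scored a failure, and at any baseline above 7.5 mg/day a patient who cuts by 7.5 mg or less while staying above 7.5 mg/day is scored a success. True successes are also lost at baselines above 7.5 and up to 15 mg/day when the cut exceeds 7.5 mg.

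The effect is confined to the supplemental PPCV and PP analyses of this variable. This rests on reading dose reduction as baseline minus current dose, as the adjacent rows do. The number of patients affected cannot be given, because the SAP does not report the distribution of baseline or later doses.

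**What to change.** Reconcile the third steroid-sparing derivation in Table JAIA.6.4 with the SAP's own variable name and Table JAIA.6.6, so that it tests whether the prednisone-equivalent daily dose is at or below 7.5 mg throughout the period from the Week 40 visit to the Week 52 visit. This adds no new rule, and Section 6.9 already derives a daily dose for each study day. If programs already exist, check that every success on the major secondary sparing variable is also a success on this one within the same datapoint set. The cost is one sentence and that check, with no statistical downside.
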